## ABBREVIATIONS AND DEFINITIONS OF TERMS

AE	Adverse event
AYA	Adolescent and Young Adult
BEAM	Behavioral Economics for Activity Motivation trial
BMI	Body mass index
BREQ-3	Behavioral Regulation in Exercise Questionnaire-3
mHealth	Mobile Health
MCQ	Monetary Choice Questionnaire
MVPA	Moderate to vigorous physical activity
PCTRC	Pediatric Clinical and Translational Research Center
PHI	Protected Health Information
RAI	Relative Autonomy Index
SAE	Serious adverse event
T2D	Type 2 Diabetes
W2H	Way to Health

---

## ABSTRACT

**Context:** There is an urgent need to engineer targeted physical activity interventions that are effective and scalable for obese adolescents and young adults (AYA) with type 2 diabetes (T2D), who often have very low levels of physical activity. The BEAM Trial is a proposed mobile health (mHealth) intervention that uses behavioral economic-informed financial incentives and text messaging to promote physical activity in AYA with T2D and prediabetes.

**Objectives:** The primary objective is to determine the main and interactive effects of four intervention components (“factors”) on time spent in moderate to vigorous physical activity (MVPA). Secondary objectives include to determine the main and interactive effects of the four intervention components on steps per day, body mass index Z-score; hemoglobin A1c; fasting insulin, glucose, triglycerides, LDL, and HDL; and liver enzymes (AST, ALT).

**Study Design:** 2 full factorial trial; participants randomized to one of 16 experimental conditions (combination of 4 factors with 2 levels each: 1) text messages sent (a) once daily, or (b) twice daily; 2) financial incentives that are (a) loss- or (b) gain-framed; 3) step count goals set as (a) weekly or (b) daily; and 4) step count goal set as (a) ramped or (b) fixed)

**Setting/Participants:** 13-22 year-old AYA who are overweight or obese (BMI $\geq$ 85th percentile for age/sex, or  $\geq$ 25 kg/m^2 if  $\geq$ 18 years old), have prediabetes or type 2 diabetes, and attend the Endocrinology or Adolescent Medicine outpatient clinic at the Children’s Hospital of Pittsburgh; 75 participants will be recruited.

**Study Interventions and Measures:** Vitals, body size measurement, pubertal status, medical history, nutrition, physical activity questionnaires, behavioral questionnaires, and laboratory assessments will be assessed at two in-person study visits; labs (insulin, glucose, hemoglobin A1c, lipids, liver enzymes) will be collected after overnight fast. The primary outcome of MVPA and secondary outcome of step count will be measured using Fitbit physical activity trackers worn daily during a 12-week intervention, which will take place after a 2-week run-in.

---

---

## PROTOCOL SYNOPSIS

Study Title	Behavioral Economics for Activity Motivation in Adolescents and Young Adults with Prediabetes and Type 2 Diabetes Trial
Funder	National Institutes of Health
Study Rationale	Early intervention to reduce risks associated with youth-onset type 2 diabetes (T2D) is critical due to high rates of cardiovascular comorbidities early in the disease and a 15-year reduction in life expectancy. Due to the difficulty of treating T2D in younger people and the more rapid progression of disease, efforts to prevent disease progression in young people with prediabetes, and new and better ways to treat and prevent T2D in youth are needed. The proposed study uses a highly efficient experimental design to investigate multiple potential intervention components, such as text messages and behavioral economic-based financial incentives, aimed at creating an engaging, effective intervention.
Study Objective(s)	Primary: to determine the impact of each intervention component on time spent in moderate to vigorous physical activity (MVPA). Secondary: to determine the impact of each intervention component on daily step count; body mass index Z-score; hemoglobin A1c; fasting insulin, glucose, triglycerides, LDL, HDL; liver enzymes.
Test Article	Each participant will be randomized to 1 combination of 4 intervention components, each with two levels. The four intervention components are: 1) text messages sent (a) once daily or (b) twice daily; 2) financial incentives framed as (a) losses or (b) gains; 3) step count goals set as (a) weekly or (b) daily goals; and 4) step count goals: (a) ramped up gradually or (b) set at a fixed goal throughout the intervention.
Study Design	Factorial trial
Subject Population	Inclusion Criteria
key criteria for Inclusion and Exclusion:	
 
1. Males or females age 13 to 22 years
 
2. Overweight or obese (<math>BMI \geq 85^{\text{th}} \text{ percentile for age/sex, or } \geq 25 \text{ kg/m}^2</math> for participants <math>\geq 18</math> years)
 
3. Diagnosis with a condition associated with insulin resistance, including prediabetes or type 2 diabetes
 
4. Consent (adult subjects), parental/guardian permission (if applicable), assent (if applicable)
 
5. Willingness to wear Fitbit during waking hours daily for duration of run-in and intervention
 
6. Possession of a smartphone with data plan.
 

---

---

**Exclusion Criteria**

7. Potential subject unable to speak or read in English
8. Severe cognitive impairment
9. Permanent or temporary physical disability that impairs ambulation or precludes engagement in MVPA
10. Current pregnancy
11. Previously-diagnosed or current restrictive or purging eating disorder
12. MVPA>30 minutes per day or Fitbit wear < 4 days during second week of 2-week run-in period

---

Number Of Subjects	75 total, all at Children's Hospital of Pittsburgh
Study Duration	Each participant will attend 2 in-person study visits that will last 2-3 hours each. The duration from study entry to completion will be no longer than 17 weeks.
Study Phases	
Screening and recruitment: Potential subjects will be identified via review of Endocrinology clinic schedules weekly and by using the CAYAH RESEARCH INTEREST FORM distributed by Adolescent medicine. After potential subjects are identified, they will be contacted along with their parents/guardians (as applicable), to screen for eligibility. Subjects will be consented and will be scheduled for a morning study visit at the Pediatric Clinical and Translational Research Center (PCTRC). They will be instructed to complete an overnight 12 hour fast at home prior to the study visit.
 
Visit 1 (in-person): Participants will undergo fasting laboratory evaluations, vitals, anthropometry, pubertal status, medical history, and physical activity and behavioral questionnaires. Participants will be given Fitbit physical activity trackers to wear for the duration of the study during waking hours and will be instructed on use.
 
Run-In: Participants will wear the Fitbit daily during waking hours for 14 consecutive days. They will receive daily reminder text messages to wear the Fitbit. At the end of 14 days, mean daily MVPA and number of days Fitbit was worn during days 8-14 will be determined. Participants will be excluded if their MVPA was >30 minutes/day or Fitbit wear was <4 days. Eligible participants will be randomized to 1 of 16 experimental conditions (4 factors, 2 levels each = <math>4^2=16</math>) and step count goals assigned.
 
Visit 2: Randomized participants will be called to review step goal; ineligible participants will be called to inform of study completion and will be asked to return the Fitbit via prepaid envelope.
 
Intervention: Participants will wear Fitbits daily for 12 weeks. Three nutrition recalls will be conducted via phone (weeks 1-2). A

---

---

safety check phone call (**Visit 3**) will take place during week 2 and another safety check and step count goal review phone call will take place during week 6 (**Visit 4**).

**Visit 5 (in-person):** After a 12-hour overnight fast at home, participants will attend the final study visit to undergo fasting laboratory evaluations, vitals, anthropometry, and exit interviews. Participants will return the Fitbit physical activity trackers.

---

Efficacy Evaluations	Change in minutes spent in MVPA (primary) and daily step count (secondary) from baseline to intervention week 12
Safety Evaluations	Adverse events are not anticipated. Any AEs and SAEs will be reported to IRB within the allotted timeframe.
Statistical And Analytic Plan	
Demographic and clinical characteristics of subjects will be described using summary statistics, including means, standard deviations, medians, and ranges for continuous variables, and frequencies and percentages of participants for categorical variables. Data will be assessed for outliers. Scatter plots and box plots will be used to examine the relationship between independent (e.g. individual characteristics or component level, such as gain versus loss-framed incentives) and dependent variables. Longitudinal data will be summarized by factor level (e.g. loss-framed versus gain-framed incentives). Statistical analyses will be conducted using Stata 17 or R: A language and environment for statistical computing. The significance level for two-sided hypothesis testing will be set at 0.05.
 
Effect coding will be used to represent each factor level (e.g. -1 for loss-framed and +1 for gain-framed financial incentives). ANOVA will be used to evaluate main and interactive effects of intervention components and component levels on the primary outcome of change in MVPA from baseline to 12 weeks, as well as secondary outcomes of change in BMI Z-score, fasting insulin, triglycerides, LDL and HDL from Visits 1 to 5. Main and interactive effects that demonstrate an increase in MVPA of <math>\geq 15</math> minutes per day from baseline to week 12 will be considered effective. The main and interactive effects of intervention components on change in MVPA from baseline to 6 weeks (mid-point) will also be explored using ANOVA.

DATA AND SAFETY MONITORING PLAN	The study team will be responsible for data management and collection and are responsible for the accuracy and completeness. Only investigators and study team members that have completed appropriate IRB training/approval are eligible to collect and work on information collected from this study. Data will be entered directly into REDCap by the study team or by participants when responding to surveys. In order to guard against disclosure of PHI, each study participant will be assigned a unique identification code.

---

[figure not shown]
---

The code will be kept in a password-protected file on the PI's  
University-managed secure server.

---

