##### 3.1.3 Run-In

To determine baseline physical activity (MVPA), participants will be asked to wear the provided Fitbit for 14 consecutive days during waking hours and to sync the Fitbit daily with the app on their smartphone. They will also receive reminder text messages twice daily. Participants with mean daily MVPA >30 minutes or with < 4 days of Fitbit wear during the second week of run-in will be withdrawn from the study and will not continue on with the intervention. All participants will be called by phone (Visit 2) to review whether they will proceed to the intervention or not. Withdrawn participants will be asked to return the Fitbit using a prepaid envelop.

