## 4.3 Run-In and Randomization

### 4.3.1 2-Week Run-In

- Participant wears Fitbit daily during waking hours and syncs daily with smartphone
- Daily text message reminder sent to participant
- On day 15, study team will evaluate MVPA during days 8-14
  - Exclude from intervention if mean > 30 minutes/day or if < 4 days with evaluable Fitbit data
- Calculate mean daily step count during days 8-14, to provide to participant for reference

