### 6.4 Control of Bias and Confounding

Potentially eligible subjects will be stratified by sex and age (13-18, 19-22), and an equal number of participants will be contacted per group until recruitment goals are reached or all potentially eligible subjects in a category are enrolled or decline to participate.

Multivariable models will adjust for covariates including age, sex, race, ethnicity, disease type (prediabetes versus diabetes), baseline laboratory values, anthropometrics (e.g. BMI-Z), and baseline activity level. The distribution of measured motivation characteristics and delay discounting tendencies will be assessed across intervention components (e.g., proportion with high measures of intrinsic motivation among those randomized to loss-framed versus those randomized gain-framed incentives) will be assessed. If imbalanced across components, these measures will be included in multivariable models.

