## 6.5 Statistical Methods

### 6.5.1 Analysis of Primary and Secondary Outcomes of Interest

Descriptive and visual statistics: Demographic and clinical characteristics of subjects will be described using summary statistics, including means, standard deviations, medians, and ranges for continuous variables, and frequencies and percentages of participants for categorical variables. Data will be assessed for outliers. Scatter plots and box plots will be used to examine the relationship between independent (e.g. individual characteristics such as age, prediabetes versus T2D, race/ethnicity; as well as component level, such as gain versus loss-framed incentives) and dependent variables. Line plots will be generated for the primary outcome of daily MVPA, with one line per subject and an overall trend line. Longitudinal data will be summarized by factor level (e.g. loss-framed versus gain-framed incentives). Statistical analyses will be conducted using Stata 17 (StataCorp, College Station, TX) or R: A language and environment for statistical computing (R Corp Team, Vienna, Austria). The significance level for two-sided hypothesis testing will be set at 0.05.

Main Effects and Interactions: The trial is a  $2^4$  full factorial design (4 factors with 2 levels each), resulting in 16 experimental conditions. **Importantly, this is not a 16-arm randomized control trial:** in factorial designs, subjects are “recycled,” allowing for the N per level (e.g. subjects randomized to loss-framing) to be the relevant value rather than the n per experimental condition.(Collins 2018) Effect coding will be used to represent each factor level (e.g. -1 for loss-framed and +1 for gain-framed).(Collins, Dziak et al. 2014) Effect coding allows effect estimates to be uncorrelated when the factorial study is balanced, which allows hypothesis tests to be independent.(Collins 2018) With effect coding, beta coefficient standard errors are equal, so in a balanced design, the power to detect each coefficient is the same.

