#### 6.6 Sample Size and Power

To determine sample size, the MOST R package (FactorialPowerPlan) was used.(Collins, Huang et al. 2017) Using a sample size of 64, 4 factors (n=16/factor, n=4/experimental condition), and two-sided alpha = 0.05, we will have at least 80% power to detect a 15-minute change in MVPA assuming a standard deviation of 20 minutes(Kriska, Delahanty et al. 2013) (**Table 2**). To allow for 64 evaluable subjects, we will recruit 75 AYA (anticipated dropout rate of 15%). In 2020, the Children's Hospital of Pittsburgh Division of Pediatric Endocrinology, Metabolism, and Diabetes followed approximately 2200 patients, approximately 10% (~220) of whom have type 2 diabetes. The vast majority of youth with type 2 diabetes are in the adolescent age range that will be targeted in this intervention. In addition, a variable number of youth with prediabetes are seen by the Division. Based on this, a total sample size of 75 is feasible to enroll over the planned study period. For secondary outcomes including BMI Z-score, labs, and Healthy Eating Index, using a sample size of 64, 4 factors, and two-sided alpha = 0.05, we will have at least 80% power to detect a standardized regression coefficient of 0.36.

**Table 2.** Effect size and power estimates (N=64)

Δ	SD	Effect size	α	Power
15	20	0.38	0.05	0.84
15	20	0.38	0.1	0.91

-	-	0.36	0.05	0.80
-	-	0.32	0.1	0.80

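### Days 1-7 of the run-in have no stated analytic use; a baseline covariate built from all valid run-in days would be a small, free gain in precision

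*Combined protocol and SAP*

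**What the plan says.** Section 3.1.3 ties the whole run-in to baseline: "To determine baseline physical activity (MVPA), participants will be asked to wear the provided Fitbit for 14 consecutive days during waking hours". The evaluation step is narrower. Section 4.3.1 says "On day 15, study team will evaluate MVPA during days 8-14", and the Synopsis (Study Phases, Run-In) agrees: "At the end of 14 days, mean daily MVPA and number of days Fitbit was worn during days 8-14 will be determined". Both describe the eligibility check, which excludes a mean above 30 minutes/day or fewer than 4 days of data. Section 4.3.1 also computes a days 8-14 step mean to give to the participant.

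In Table 1 of section 6.5.3 the step rows define baseline as the second run-in week. The MVPA rows say only baseline, with no window.

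The role of baseline in the primary model varies by section:
- 6.5.1 and the Synopsis: ANOVA of change from baseline to week 12.
- 6.1: the week-12 mean itself.
- Table 1: ANOVA/ANCOVA.
- 6.4: adjusts for several covariates, ending with "anthropometrics (e.g. BMI-Z), and baseline activity level".
- 8.1.1: would consider covariates such as baseline activity only if they differ across component levels.

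Section 6.5.4 uses baseline daily MVPA minutes as an imputation predictor.

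**The concern.** Daily MVPA varies a good deal within a person, so a mean over 4 to 7 days measures usual activity with appreciable error. Seven more days are already recorded, before randomisation, on the same device. Leaving them out makes the baseline variable noisier than it need be. In ANCOVA a noisier covariate explains less of the week-12 outcome. In a change score the baseline error enters at full weight.

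A first week with a new tracker may be untypical. That is a fair reason not to judge eligibility on it or to measure change from it. It is a weaker reason to discard it as a covariate, since any variable fixed before randomisation leaves the factor contrasts unbiased. At stake is a little precision on the MVPA and step contrasts in a trial of 64 evaluable participants.

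**Working it through.** **1. The plan's own power.** Inputs from section 6.6: "Using a sample size of 64, 4 factors (n=16/factor, n=4/experimental condition"), and 80% power or more "to detect a 15-minute change in MVPA assuming a standard deviation of 20 minutes". Section 6.5.1: "The significance level for two-sided hypothesis testing will be set at 0.05". For one effect-coded coefficient the noncentrality is λ = N × (Δ / 2SD)² = 64 × (15/40)² = 64 × 0.375² = 9.
- Main effects only, 64 − 5 = 59 df: power 0.839.
- 16 parameters, 48 df: power 0.836.

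Table 2 states 0.84, so it reproduces. It needs 32 participants per factor level, which the text's 16 per factor does not describe. No baseline covariate enters this calculation, so 0.84 does not depend on the run-in window.

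**2. Reliability of the baseline mean.** Spearman-Brown: R(k) = k × ICC / (1 + (k − 1) × ICC). The single-day ICC is an assumption.

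| Valid days | ICC 0.2 | ICC 0.4 |
|---|---|---|
| 4 | 0.50 | 0.73 |
| 7 | 0.64 | 0.82 |
| 14 | 0.78 | 0.90 |

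These values are before the eligibility limit is applied.

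**3. Effect on adjusted variance.** This was simulated with the 30-minute limit applied to week 2, comparing the 14-day mean with the days 8-14 mean as covariate. All variance inputs are assumptions.
- Gamma person means of 15-25 min/day (SD 12-16), day-to-day SD 12-20, week-level SD 4-6, true-change SD 10-18, first-week novelty of +10-20% with person-specific SD 0-8, 6 valid days per week; 4,000 trials of N = 64. The variance ratio is 0.90-0.97, a cut of 3-10%. Entering the two weekly means separately gives 0.93-0.99.
- Further gamma-based runs of 600,000 persons: a cut of 4-8% with novelty SD 0-8 min, and 2% with an extreme novelty SD of 12 min.
- Runs scaled so that the change SD is 20 (mean 22 min, between-person SD 8-12, ICC 0.2-0.4, 0-15% of within-person variance at week level): ANCOVA gains 0.4 to 2.1 power points. Two lognormal cases without a week-level effect show the spread. Between-person SD 12 with ICC 0.2 takes the residual SD from 19.25 to 18.96, a variance cut of 1 − (18.96/19.25)² = 3%. Between-person SD 8 with ICC 0.4 takes it from 19.92 to 19.81, a cut of 1%.

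**4. Power for the protocol's effect.** Take 20 as the residual SD with the days 8-14 covariate. A fractional cut c gives λ = 9/(1 − c), at 48 df.

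| c | λ | Power |
|---|---|---|
| 0 | 9.00 | 0.836 |
| 0.02 | 9.18 | 0.844 |
| 0.03 | 9.28 | 0.847 |
| 0.08 | 9.78 | 0.865 |
| 0.10 | 10.00 | 0.873 |

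In participants, 64/0.98 = 65.3 and 64/0.90 = 71.1, so the gain is worth about 1 to 7 people. If the outcome stays an unadjusted change score, moving its baseline from 7 to 14 days lowers the SD from 20.0 to 18.8-19.8 in the scaled runs. Power then goes from 0.837 to 0.843-0.878.

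**5. Does the 30-minute limit cost precision?** Lognormal case, between-person SD 12, ICC 0.4, no week-level effect, days 8-14 covariate:

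| | Week-12 SD | Residual SD | R² = 1 − (residual SD / week-12 SD)² |
|---|---|---|---|
| No limit | 22.69 | 19.92 | 0.23 |
| Limit applied | 20.32 | 19.79 | 0.05 |

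R² falls sharply because the outcome variance falls too. The residual SD, which sets the precision of the contrasts, does not rise. A normal model gives 18.83 without and 18.82 with the limit; gamma models give 17.7 and 17.4, 13.1 and 12.9, 22.4 and 21.9.

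**The case against.** Using the second week after a week of acclimatisation is a reasonable design choice. Sections 3.1.2 and 4.2 place coaching on an activity plan at Visit 1, just before week 1, so reactivity that differs between people is plausible then. Days 1-7 also carry no minimum-wear requirement and may be sparse. Section 6.4 lists other covariates (age, sex, disease type, BMI-Z and more) that could overlap with the extra week. All of this stands, and it shrinks the gain. It does not make the first week harmful as a covariate: the gain stayed positive even with a strongly person-specific first week.

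Three stronger readings are tempting, and the documents do not support them.
- A reader might infer that the eligibility limit, by narrowing the baseline range, costs precision. It lowers the covariate's R² but not the precision of the factor contrasts (step 5).
- A reader might infer that the plan fixes days 8-14 as the MVPA baseline. It does so for steps only. For MVPA the window is inferred from the eligibility check and from the weekly mean in section 6.5.1, while section 3.1.3 points to the full 14 days.
- A reader might infer that the primary analysis is biased or its power misstated. Neither follows: randomised contrasts are unbiased with either window, and 0.84 reproduces without any covariate.

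It is also fair to say that the documents have not settled whether baseline is a covariate at all. That comes first, and the fix deals with both.

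**Conclusion.** The point holds as a modest, free improvement of low severity. Days 1-7 are collected before randomisation and have no stated analytic use. A covariate from all valid run-in days is more reliable than one from 4 to 7 days. The expected reduction in adjusted variance is roughly 2-10%, about 1 to 4 power points at most for 15 minutes with SD 20; the least favourable scaled case gave about 1%. These sizes rest on assumed day-to-day, week-to-week and between-person variation, because the documents give none, and on the first week being reasonably well worn. No bias or invalid inference is shown.

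**What to change.** 1. Keep days 8-14 for the eligibility check and for describing change, and state the MVPA baseline window explicitly, as Table 1 does for steps.
2. Pre-specify ANCOVA of week-12 mean MVPA and of week-12 mean steps, with the mean of all valid run-in days 1-14 of the same measure as the baseline covariate. Include it whether or not baseline is imbalanced, which removes the difference between sections 6.4 and 8.1.1. Define a valid day once for the run-in. A participant with no valid day in days 1-7 keeps the days 8-14 mean.
3. If change from days 8-14 remains the outcome, enter the days 1-7 and days 8-14 means as two covariates.
4. Use the same baseline variable as the predictor in the imputation model of section 6.5.4.

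The cost is SAP wording only, as the data are already collected. The single 14-day mean uses no more degrees of freedom than the 7-day mean; two weekly means use one more.
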